## 4.3 Justification for Dose

The proposed MK-6482 dose for this trial is 80 mg daily. Since MK-6482 clearance is predicted to occur predominantly by hepatic metabolism, MK-6482 exposures in patients with moderate hepatic impairment are anticipated to be increased compared to healthy control participants. Based on a population PK analysis using concentration data across multiple MK-6482 clinical studies, the geometric mean for steady-state AUC for 120 mg daily is ~1.37-fold for participants categorized as having mild hepatic impairment (N=8) using the NCI classification compared to participants with normal hepatic function (N=109) (23.34  $\mu$ g\*h/mL versus 17.06  $\mu$ g\*h/mL). By leveraging the previously reported relationship between Child Pugh and NCI classifications (Elmeliegy M et al. 2021), the geometric mean for steady-state AUC for MK-6482 120 mg daily is estimated to be ~2.13-fold for participants categorized as having moderate hepatic impairment (Child-Pugh B) compared to participants with normal hepatic function (36.29  $\mu$ g\*h/mL versus 17.06  $\mu$ g\*h/mL). To minimize the possibility of exposing participants with moderate hepatic impairment to

unanticipated higher exposures, a lower dose (80 mg) than the clinical dose for MK-6482 (120 mg) will be evaluated in this trial.

Multiple daily doses of 240 mg daily and 120 mg twice daily of MK-6482 have been administered to patients with advanced solid tumors, which were associated with 1.5 and 2.3-fold increases in AUC compared to 120 mg, respectively. The predicted higher exposures following a single 80 mg dose in patients with moderate hepatic impairment are within the range of observed exposures in the MK-6482 clinical development program.

## 4.4 Beginning and End-of-Study Definition

The overall study begins when the first participant (or their legally acceptable representative) provides documented informed consent. The overall study ends when the last participant completes the last study-related contact, withdraws consent, or is lost to follow-up (ie, the participant is unable to be contacted by the investigator).

A study may be paused during review of newly available preclinical/clinical safety, PK, pharmacodynamic, efficacy, or biologic data or other items of interest, prior to a final decision on continuation or termination of the study. It may be necessary to keep the study open for gathering/reviewing of additional supportive data to optimally complete the objective(s) of the study. If necessary, the appropriate amendment(s) to the protocol and/or appropriate communication(s) will be generated. If the decision has been made to end the study following this review period, the study end will be defined as the date of the Sponsor decision, and this end of study date supersedes the definitions outlined above. The Competent Authority(ies) and IRB(s)/IEC(s) will be apprised of the maximum duration of the study beyond the last participant out and the justification for keeping the study open.

## 4.4.1 Clinical Criteria for Early Study Termination

There are no prespecified criteria for terminating the study early.

## 5 STUDY POPULATION

Vasectomized or surgically sterilized male participants and female participants of nonchildbearing potential between the ages of 18 and 75 years (inclusive) will be enrolled in this study.

Participants with normal hepatic function will match to the mean demographic parameters of the moderate hepatic impairment group. Healthy control participants will be matched for the mean age ( $\pm$  15 years), mean BMI ( $\pm$ 20%), sex (similar males/female ratio in each group), and UGT2B17 genotype (at least 2 IMs and 2 EMs in each group). If a UGT2B17 PM moderate hepatic impairment participant is enrolled in the study, a UGT2B17 PM healthy matched control participant will be included. If after reasonable efforts, a UGT2B17 PM healthy matched control participant is not enrolled, an additional participant with moderate hepatic impairment (ie, a 9th moderate hepatic impairment participant be participant), who is not UGT2B17 PM, will be enrolled. This additional moderate hepatic impairment participant should be

matched to the mean age ( $\pm$  15 years) and BMI ( $\pm$  20%) of the other 8 hepatically impaired participants. The final healthy matched control participant (ie, the 8th healthy control participant), who is also not UGT2B17 PM, should also be matched to the mean age ( $\pm$  15 years), BMI ( $\pm$  20%), and sex (with a similar male/female ratio in each group) of the 8 moderate hepatic impairment participants (ie, not including the 9th hepatically impaired participant).

Prospective approval of protocol deviations to recruitment and enrollment criteria, also known as protocol waivers or exemptions, is not permitted.

## 5.1 Inclusion Criteria

## 5.1.1 Inclusion Criteria for Participants With Healthy Hepatic Function

A participant will be eligible for inclusion in the study if the participant meets all of the following criteria:

## Type of Participant and Disease Characteristics

- 1. Is in good health based on medical history, physical examination, vital sign measurements, and ECGs performed at the prestudy (screening) visit and before administration of study intervention.
- 2. Is in good health based on laboratory safety tests obtained at the prestudy (screening) visit and before administration of study intervention. Appendix 2 provides a table of laboratory safety tests to be performed. Appendix 9 provides an algorithm for the assessment of out-of-range laboratory values.
- 3. Has a BMI 18.0-40.0 kg/m^2, inclusive. See Section 8.3.1 for criteria on rounding to the nearest whole number. BMI = weight (kg)/height (m). BMI must be within  $\pm$  20% of the mean BMI in the hepatic impairment group.

## **Demographics**

4. Is male or female, from 18 years to 75 years of age inclusive, at the time of signing the informed consent. Age must be within  $\pm$  15 years of the mean age in the hepatic impairment group.

## **Male Participants**

- 5. Male participants are eligible to participate if they have been vasectomized or undergone surgical sterilization for at least 4 months or more prior to study intervention administration and agree to the following during the intervention period and for at least 7 days (time needed for MK-6482 to be eliminated) after administration of study intervention:
  - Be abstinent from heterosexual intercourse as their preferred and usual lifestyle (abstinent on a long-term and persistent basis) and agree to remain abstinent

OR

- Must agree to use contraception as detailed below:
  - Agree to use a male condom plus partner use of an additional contraceptive method when having penile-vaginal intercourse with a WOCBP who is not currently pregnant. Note: Men with a pregnant or breastfeeding partner must agree to remain abstinent from penile-vaginal intercourse or use a male condom during each episode of penile-vaginal penetration.

Contraceptive use by men should be consistent with local regulations regarding the methods of contraception for those participating in clinical studies.

#### **Female Participants**

- 6. A female participant is eligible to participate if:
  - She is a WONCBP, as defined in Appendix 5.

## **Informed Consent**

7. The participant (or legally acceptable representative) has provided documented informed consent for the study. The participant may also provide consent for FBR. However, the participant may participate in the study without participating in FBR.

#### 5.1.2 Inclusion Criteria for Participants With Moderate Hepatic Impairment

A participant will be eligible for inclusion in the study if the participant meets all of the following criteria:

## Type of Participant and Disease Characteristics

- 1. With exception of the hepatic impairment, is in good health, in the opinion of the investigator, based on medical history, physical examination, vital sign measurements, and ECGs performed at the prestudy (screening) visit and before administration of the study intervention.
- 2. With exception of the hepatic impairment, is in good health, in the opinion of the investigator, based on laboratory safety tests obtained at the prestudy (screening) visit and before administration of study intervention. Appendix 2 provides a table of laboratory safety tests to be performed. Appendix 9 provides an algorithm for the assessment of out-of-range laboratory values.
- 3. Has a BMI 18.0-40.0 kg/m^2, inclusive. See Section 8.3.1 for criteria on rounding to the nearest whole number. BMI = weight (kg)/height (m).
- 4. Has a score on the Child-Pugh scale of B (a score of 7-9 on Child-Pugh Score) at the prestudy (screening) visit. At least five (5) participants with moderate hepatic impairment will be required to have total bilirubin range within >1.5X ULN and ≤3X ULN.

5. Has a diagnosis of chronic (>6 months), stable (no acute episodes of illness within the previous 30 days from administration of study intervention due to deterioration in hepatic function) hepatic impairment.

#### **Demographics**

6. Is male or female, from 18 years to 75 years of age inclusive, at the time of signing the informed consent.

#### Male Participants

- Male participants are eligible to participate if they have been vasectomized or undergone surgical sterilization for at least 4 months or more prior to study intervention administration and agree to the following during the intervention period and for at least 7 days (time needed for MK-6482 to be eliminated) after administration of study intervention:
  - Be abstinent from heterosexual intercourse as their preferred and usual lifestyle (abstinent on a long-term and persistent basis) and agree to remain abstinent

OR

- Must agree to use contraception as detailed below:
  - Agree to use a male condom plus partner use of an additional contraceptive method when having penile-vaginal intercourse with a WOCBP who is not currently pregnant. Note: Men with a pregnant or breastfeeding partner must agree to remain abstinent from penile-vaginal intercourse or use a male condom during each episode of penile-vaginal penetration.

Contraceptive use by men should be consistent with local regulations regarding the methods of contraception for those participating in clinical studies.

#### **Female Participants**

- 8. A female participant is eligible to participate if:
  - She is a WONCBP, as defined in Appendix 5.

#### **Informed Consent**

9. The participant (or legally acceptable representative) has provided documented informed consent for the study. The participant may also provide consent for FBR. However, the participant may participate in the study without participating in FBR.

## 5.2 Exclusion Criteria

## 5.2.1 Exclusion Criteria for Participants with Healthy Hepatic Function

The participant must be excluded from the study if the participant meets any of the following criteria:

## **Medical Conditions**

- 1. Has a history of clinically significant endocrine, GI, cardiovascular, hematological, hepatic, immunological, renal, respiratory, genitourinary, or major neurological (including stroke and chronic seizures) abnormalities or diseases. Participants with a remote history of uncomplicated medical events (eg, uncomplicated kidney stones, as defined as spontaneous passage and no recurrence in the last 5 years from administration of study intervention, or childhood asthma) may be enrolled in the study at the discretion of the investigator.
- 2. Is mentally or legally incapacitated, has significant emotional problems at the time of prestudy (screening) visit or expected during the conduct of the study or has a history of clinically significant psychiatric disorder of the last 5 years from administration of study intervention. Participants who have had situational depression may be enrolled in the study at the discretion of the investigator.
- 3. Has a history of cancer (malignancy).

Exceptions: (1) Adequately treated nonmelanomatous skin carcinoma or carcinoma in situ of the cervix or; (2) Other malignancies that have been successfully treated with appropriate follow up and therefore unlikely to recur for the duration of the study, in the opinion of the investigator and with agreement of the Sponsor (eg, malignancies that have been successfully treated  $\geq 10$  years prior to the prestudy [screening] visit).

4. Has an estimated  $CrCl \leq 70$  mL/min based on the CG Equation.

## **Cockcroft-Gault Equation:**

CrCl = (140-age[yr])(body wt [kg]) (72)(serum creatinine [mg/dL])

[When creatinine is measured in µmol/L, use this formula]

CrCl = (140-age[yr])(body wt[kg])(72)(serum creatinine [µmol/L] x 0.0113)

For females, multiply the result by 0.85.

At the discretion of the investigator a measured CrCl, as determined by a 24-hour urine collection, may be used in place of, or in conjunction with, the estimate of the CrCl.

- 5. Has a history of significant multiple and/or severe allergies (eg, food, drug, latex allergy), or has had an anaphylactic reaction or significant intolerability (ie, systemic allergic reaction) to prescription or nonprescription drugs or food.
- 6. Is positive for HBsAg, hepatitis C antibodies, or HIV.
- 7. Had major surgery, donated or lost 1 unit of blood (approximately 500 mL) within 4 weeks prior to the prestudy (screening) visit.

#### **Prior/Concomitant Therapy**

- 8. Is unable to refrain from or anticipates the use of any medication, including prescription and nonprescription drugs (with the exception of prescription drugs that are approved by the investigator and Sponsor) or herbal remedies as indicated in Section 6.5 for the prohibited period of time. There may be certain medications that are permitted (see Section 6.5).
- 9. Has received any nonlive vaccine starting from 14 days prior to study intervention or is scheduled to receive any nonlive vaccine through 30 days following study intervention. Exception: COVID-19 vaccine may be administered. Study intervention must be given at least 72 hours following or at least 48 hours prior to any COVID-19 vaccination.

#### **Prior/Concurrent Clinical Study Experience**

10. Has participated in another investigational study within 4 weeks (or 5 half-lives, whichever is greater) prior to study intervention administration. The window will be derived from the date of the last study intervention administration in the previous study.

#### **Diagnostic Assessments**

- 11. Has a UGT2B17 and CYP2C19 genotype consistent with a dual poor metabolizer phenotype.
- 12. Has hemoglobin level below the lower limit of the normal range at the prestudy (screening visit) or check-in.
- 13. Has a pulse oximetry reading <92% at rest at the prestudy (screening visit) or check-in.
- 14. Has a QTc interval >470 msec at the prestudy (screening visit) or check-in, has a history of risk factors for Torsades de Pointes (eg, heart failure/cardiomyopathy or family history of long QT syndrome), has uncorrected hypokalemia or hypomagnesemia, is taking concomitant medications that prolong the QT/QTc interval.

#### **Other Exclusions**

- 15. Is under the age of legal consent.
- 16. Is a heavy smoker or heavy user of nicotine-containing products (>20 cigarettes or equivalent/day).
- 17. Smokers who do not agree to consume  $\leq 10$  cigarettes or equivalent/day from the time of the prestudy (screening) visit and until the last PK sample collection.

- Consumes greater than 3 glasses of alcoholic beverages (1 glass is approximately equivalent to: beer [354 mL/12 ounces], wine [118 mL/4 ounces], or distilled spirits [29.5 mL/1 ounce]) per day. Participants who consume 4 glasses of alcoholic beverages per day may be enrolled at the discretion of the investigator.
- 19. Consumes excessive amounts, defined as greater than 6 servings (1 serving is approximately equivalent to 120 mg of caffeine) of coffee, tea, cola, energy drinks, or other caffeinated beverages per day.
- 20. Is a regular user of cannabis, any illicit drugs or has a history of drug (including alcohol) abuse within approximately 2 years prior to the prestudy (screening) visit. Participants must have a negative drug screen at the prestudy (screening) visit or before administration of study intervention.
- 21. Presents any concern by the investigator regarding safe participation in the study or for any other reason the investigator considers the participant inappropriate for participation in the study.
- 22. Is unwilling to comply with the study restrictions (see Section 5.3 for a complete summary of study restrictions).
- 23. Is or has an immediate family member (eg, spouse, parent/legal guardian, sibling, or child) who is investigational site or Sponsor staff directly involved with this study.

## 5.2.2 Exclusion Criteria for Participants With Moderate Hepatic Impairment

The participant must be excluded from the study if the participant meets any of the following criteria:

## **Medical Conditions**

- 1. Is mentally or legally incapacitated, has significant emotional problems at the time of prestudy (screening) visit or expected during the conduct of the study or has a history of clinically significant psychiatric disorder of the last 5 years from administration of study intervention. Participants who have had situational depression may be enrolled in the study at the discretion of the investigator.
- 2. Has a history of cancer (malignancy).

Exceptions: (1) Adequately treated nonmelanomatous skin carcinoma or carcinoma in situ of the cervix or; (2) Other malignancies that have been successfully treated with appropriate follow up and therefore unlikely to recur for the duration of the study, in the opinion of the investigator and with agreement of the Sponsor (eg, malignancies that have been successfully treated  $\geq 10$  years prior to the prestudy [screening] visit).

3. Has an estimated CrCl  $\leq$ 60 mL/min based on the CG Equation.

## **Cockcroft-Gault Equation:**

CrCl = (140-age[yr])(body wt [kg]) (72)(serum creatinine [mg/dL])

45

[When creatinine is measured in µmol/L, use this formula]

CrCl = (140-age[yr])(body wt[kg])(72)(serum creatinine [µmol/L] x 0.0113)

For females, multiply the result by 0.85.

At the discretion of the investigator a measured CrCl, as determined by a 24-hour urine collection, may be used in place of, or in conjunction with, the estimate of the CrCl.

- 4. Has a history of significant multiple and/or severe allergies (eg, food, drug, latex allergy), or has had an anaphylactic reaction or significant intolerability (ie, systemic allergic reaction) to prescription or nonprescription drugs or food.
- 5. Has fluctuating or rapidly deteriorating hepatic function within the prestudy (screening) period, in the opinion of the investigator.
- 6. History of liver or other solid organ transplantation.
- 7. Has transjugular intrahepatic portosystemic shunt and/or has undergone portacaval shunting.
- 8. Has encephalopathy Grade 3 or worse within 28 days before administration of study intervention.
- 9. Is positive for HIV. HBsAg positive participants are allowed to enroll if HBV DNA is below 1000 copies/mL in the plasma. Participants who are positive for HCVAb can be enrolled but must not have detectable HCV RNA in the plasma.
- 10. Had major surgery, donated or lost 1 unit of blood (approximately 500 mL) within 4 weeks prior to the prestudy (screening) visit.

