## **1.3** Schedule of Activities

|   |     |             |   |    |       | A | All G | roups |                    |   |  |
|---|-----|-------------|---|----|-------|---|-------|-------|--------------------|---|--|
|   |     |             |   | In | terve |   |       |       |                    | Notes   |  |
| Scheduled Day                                   | Scr | -1
(C-I) | 1 | 2  | 3     | 4 | 5     | 6     | Poststudy
or ET | Poststudy (follow-up) will occur approximately 14 days after study intervention administration [Sec. 8.11.4].                                       |  |
| Administrative Procedures                       |     |             |   |    |       |   |       |       |                    |   |  |
| Informed Consent                                | Х   |             |   |    |       |   |       |       |                    | Screening will occur within 28 days prior to study intervention administration [Sec. 8.1.1.1].  |  |
| Informed Consent for Future Biomedical Research | Х   |             |   |    |       |   |       |       |                    | Sec. 8.1.1.2.   |  |
| Assignment of Screening Number                  | Х   |             |   |    |       |   |       |       |                    | Sec. 8.1.7.   |  |
| Inclusion/Exclusion Criteria                    | Х   | X           |   |    |       |   |       |       |                    | Only specific criteria will be reviewed at check-in. [Sec. 5.1 and 5.2].  |  |
| Medical History                                 | Х   |             |   |    |       |   |       |       |                    | Includes review of substance usage (illicit drugs, alcohol, tobacco, and caffeine).   |  |
| Prior/Concomitant Medication Review             | Х   | Х           | Х | Х  | Х     | Х | Х     | Х     | Х                  | Sec. 6.5.   |  |
| Assignment of Treatment/Allocation
Number    |     |             | Х |    |       |   |       |       |                    | Sec. 8.1.8.   |  |
| Domiciling                                      |     | Х           | Х | Х  | Х     | Х | Х     | Х     |                    | Sec. 8.1.12.  |  |
| Safety Procedures                               |     |             |   |    |       |   |       |       |                    |   |  |
| Complete Physical Examination                   | Х   |             |   |    |       |   |       |       | Х                  | To be conducted also for participants who discontinue/withdraw from the study.  |  |

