### 4 STUDY DESIGN

### 4.1 Overall Design

This is a nonrandomized, parallel-group, multi-site, open-label study of MK-6482 in participants with moderate hepatic impairment and healthy matched control participants.

Screening of participants will occur within 28 days prior to study intervention administration.

A total of approximately 16 adult male (vasectomized or surgically sterilized) and female (non-childbearing potential only) participants will be enrolled: 8 participants with moderate hepatic impairment and 8 matched control participants with normal hepatic function.

|          | Impairment Stage  | Ν              | Child-Pugh Score a |  |  |
|----------|---|----------------|-------------------------------|--|--|
| Moderate |   | 8 b | 7-9 °                         |  |  |
| Healthy  |   | 8 b | Not applicable                |  |  |
| a.       | A Child-Pugh classification will be performed only for participants with impaired hepatic function at Screening.  |                |                               |  |  |
| b.       | At least 2 UGT2B17 IMs and at least 2 EMs will be enrolled per group.   |                |                               |  |  |
| c.       | At least five (5) participants with moderate hepatic impairment will be required to have total bilirubin within the range of >1.5X ULN and $\leq$ 3X ULN. |                |                               |  |  |

Assignment to hepatic function group will be as follows:

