#### **Prior/Concurrent Clinical Study Experience**

13. Has participated in another investigational study within 4 weeks (or 5 half-lives, whichever is greater) prior to study intervention administration. The window will be derived from the date of the last study intervention administration in the previous study.

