#### **Diagnostic Assessments**

- 14. Has a UGT2B17 and CYP2C19 genotype consistent with a dual poor metabolizer phenotype.
- 15. Has hemoglobin level below 9.5 g/dL at the prestudy (screening visit) or check-in. Participants with hemoglobin ≥9.0g/dL may be enrolled to the study at discretion of the investigator and following consultation with the Sponsor.
- 16. Has a pulse oximetry reading <92% at rest at the prestudy (screening visit) or check-in.
- 17. Has a QTc interval >480 msec at the prestudy (screening visit) or check-in, has a history of risk factors for Torsades de Pointes (eg, heart failure/cardiomyopathy or family history of long QT syndrome), has uncorrected hypokalemia or hypomagnesemia, is taking concomitant medications that prolong the QT/QTc interval.

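### The major-surgery and blood-loss exclusion is counted back from screening, so these criteria leave up to 28 days immediately before dosing uncovered (minor; cheap to close)

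*Combined protocol and SAP*

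**What the plan says.** Section 5.2.2, criterion 10 (moderate hepatic impairment) excludes a participant who "Had major surgery, donated or lost 1 unit of blood (approximately 500 mL) within 4 weeks prior to the prestudy (screening) visit". Section 5.2.1, criterion 7 (healthy controls) uses the same words.

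On timing, section 4.1 states: "Screening of participants will occur within 28 days prior to study intervention administration". The Schedule of Activities (1.3) says the same, and section 8.11.1 places screening at about 28 days before dosing.

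Other short look-back criteria end at dosing:
- Prior studies (5.2.1 criterion 10, 5.2.2 criterion 13): "Has participated in another investigational study within 4 weeks (or 5 half-lives, whichever is greater) prior to study intervention administration".
- Encephalopathy (5.2.2 criterion 8, impaired group only): "Has encephalopathy Grade 3 or worse within 28 days before administration of study intervention".
- Nonlive vaccines (5.2.1 criterion 9, 5.2.2 criterion 12): the 14-day window is also counted back from the dose.

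On re-checking, the Schedule of Activities says "Only specific criteria will be reviewed at check-in" and does not list them. Hemoglobin is one test that does reach check-in. For the impaired group the criterion reads "Has hemoglobin level below 9.5 g/dL at the prestudy (screening visit) or check-in", with entry from 9.0 g/dL possible at the investigator's discretion after consulting the Sponsor. For controls the threshold is the lower limit of normal.

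**The concern.** The purpose of a blood-loss exclusion is to keep recently depleted participants from being dosed. Counted from screening, this one reaches back to an earlier period and can omit the weeks in which a loss would matter most. Re-reading criteria 7 and 10 at check-in would not help as they stand, because an operation or donation after screening does not meet their wording.

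The point has some weight because of the drug's pharmacology. Section 2.2.2.3 names anemia due to decreased erythropoietin as an adverse drug reaction. Section 4.2.1.3 makes erythropoietin the pharmacodynamic marker, and section 8.4.7 makes an adverse event of anemia an event of clinical interest. A recent 500 mL loss could raise a participant's baseline erythropoietin and leave it still moving, so that change from baseline would mix recovery with drug effect. It could also lower the hemoglobin from which that participant enters the study.

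**Working it through.** **1. The uncovered interval.** Inputs: a 4-week (28-day) look-back from screening, and screening s days before dosing with s no greater than 28. The criterion covers s + 28 to s days before dosing, so the s days up to the dose are uncovered.

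| Screening (days before dose) | Covered (days before dose) | Uncovered |
|---|---|---|
| 28 | 56 to 28 | 28 days |
| 21 | 49 to 21 | 21 days |
| 14 | 42 to 14 | 14 days |
| 7 | 35 to 7 | 7 days |

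Both groups have the same gap. If the window also ran up to dosing, the uncovered interval would be 0 in every row.

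**2. Does the check-in hemoglobin limit close the gap?** The documents give no blood volume. Assume 4 to 6 L, full dilution after the loss and no recovery before check-in. The fractional fall is f = 500 mL / blood volume, and the lowest starting value that still passes is limit / (1 − f).

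| Assumed volume | f | Start needed for 9.5 g/dL | Start needed for 9.0 g/dL (discretionary) | Multiple of any limit |
|---|---|---|---|---|
| 6 L | 8.3% | 10.36 | 9.82 | 1.09 |
| 5 L | 10.0% | 10.56 | 10.00 | 1.11 |
| 4 L | 12.5% | 10.86 | 10.29 | 1.14 |

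An impaired participant who starts at about 10.4 to 10.9 g/dL or higher still passes 9.5 after the loss, and one who starts lower is caught. The documents give no lower limit of normal for controls. Whatever it is, a control who starts 9% to 14% above it passes; with an assumed limit of 13.5 g/dL that means about 14.7 to 15.4 g/dL. Any recovery before check-in would make passing easier. The test is a partial screen.

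**3. Do other provisions close it?**
- Good health must hold at screening and again before dosing (5.1.1 and 5.1.2, items 1 and 2), but nothing prompts a question about surgery or blood loss. The Schedule of Activities has medical history at screening only.
- Adverse events are reviewed on Day -1. Appendix 3 (10.3.1), however, says that a surgical procedure is not itself an adverse event, and a voluntary donation is not obviously one.
- The stable-disease and fluctuating-function criteria for the impaired group (5.1.2 item 5, 5.2.2 criterion 5) would catch a bleed that comes with hepatic deterioration, but not a donation or an elective operation.
- Section 5.3 contains no restriction on blood donation.
- Investigator discretion (5.2.1 criterion 21, 5.2.2 criterion 24) applies only if the investigator learns of the event.

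**4. Which results could be touched?** The primary endpoints are AUC0-inf and Cmax (9.4), and no sample size, power or precision figure depends on this criterion. Erythropoietin is a tertiary/exploratory objective (section 3) with optional summaries (9.7). Hemoglobin is a safety laboratory value. With 8 per group, one participant is 1/8 = 12.5% of a group's descriptive data. That is a share of the data, not an estimate of bias.

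**The case against.** The strongest reply is that other rules reach the period up to dosing, and this stands in part. A reader might infer that someone who loses 500 mL after screening is eligible. The documents do not support that: the participant is only not excluded by criteria 7 and 10, and may still fail on check-in hemoglobin, predose health, unstable disease, a change in medication (6.5) or investigator concern.

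A reader might also infer that the erythropoietin and hemoglobin data will be distorted. That is not shown. It needs an event in the gap that also passes check-in, and the documents give no rate for this. The erythropoietin baseline is drawn predose, after any such event, which accounts for part of the effect. The summaries are optional and descriptive, and identical wording in both groups gives no reason to expect a systematic difference, although at 8 per group a single case would fall on one side only. Section 2.2.2.3 also reports no clinically significant hemoglobin or hematocrit reductions in four completed single-dose studies, with single doses up to 200 mg; those were healthy participants, so this says less about the impaired group.

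Nor can the check-in note be read as showing that this topic is skipped, since it does not say which criteria are reviewed.

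Screening anchors do appear elsewhere: the drug-abuse window of about 2 years and the 10-year treated-malignancy example both run from screening. But a 28-day shift is small against 2 years (28/730 = 3.8%), whereas it can equal the whole of a 4-week window.

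Finally, a 500 mL loss plus the scheduled draws of 193 or 228 mL (Appendix 8) comes to 693 or 728 mL. This breaches no limit stated in the documents, because the stated maximum counts only blood collected in the study.

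**Conclusion.** The point holds as a minor gap in eligibility wording. Criteria 7 and 10 leave between 0 and 28 days before dosing uncovered, depending on when screening falls, and the full 28 days at the longest permitted interval. This part follows from the text alone.

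That the hemoglobin backstop is only partial rests on the assumed 4 to 6 L blood volume, full dilution and no recovery. The possible consequence is limited to the safety of an affected participant and to the descriptive erythropoietin, hemoglobin and anemia data. Its likelihood cannot be sized from the documents, and no effect on the primary PK comparison is shown. The change is worth making because it is cheap and delivers what the criterion appears meant to do, not because the study's main conclusion is at risk.

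**What to change.** In 5.2.1 criterion 7 and 5.2.2 criterion 10, keep the present 4-week look-back from screening and add the clause: or at any time between that visit and study intervention administration. In the Schedule of Activities, name both criteria among those reviewed at check-in. Both steps are needed, because re-checking the present wording would not catch an event after screening.

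The cost is one clause in two criteria and one question on Day -1. No procedure, sample or analysis is added, and no sample-size or precision figure changes. The downside is an occasional late screen failure.
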